## APPENDIX 1. PARTIAL DATE CONVENTIONS

Imputed dates will NOT be presented in the listings. However, in general, when calculating relative days, partial dates with missing day only will be assumed to be earliest possible date for start date (i.e. 1st of the month) and latest possible date for stop date (i.e. 31st of the month); and partial dates with both missing day and month will be assumed to be 1st January for start date or 31st December for stop date

Algorithm for Treatment-Emergent Adverse Events:

START DATE	STOP DATE	ACTION
Known	Known	If start date < first IP taken date, then not TEAE If start date >= first IP taken date, then TEAE
	Partial	If start date < first IP taken date, then not TEAE If start date >= first IP taken date, then TEAE
	Missing	If start date < first IP taken date, then not TEAE If start date >= first IP taken date, then TEAE
Partial, but known components show that it cannot be on or after first IP taken date	Known	Not TEAE
	Partial	Not TEAE
	Missing	Not TEAE
Partial, could be on or after first IP taken date	Known	If stop date < first IP taken date, then not TEAE If stop date >= first IP taken date, then TEAE
	Partial	Impute stop date as latest possible date (i.e. last day of month if day unknown or 31st December if day and month are unknown), then: If stop date < first IP taken date, then not TEAE If stop date >= first IP taken date, then TEAE
	Missing	Assumed TEAE
Missing	Known	If stop date < first IP taken date, then not TEAE If stop date >= first IP taken date, then TEAE
	Partial	Impute stop date as latest possible date (i.e. last day of month if day unknown or 31st December if day and month are unknown), then: - If stop date < first IP taken date, then not TEAE

Document: \\eedc-vnasc01\Biosdata\Archigen\SAIT101\YWA21301\Biostatistics\Documentation\SAP  
 Author:

Version Number: V2.0  
 Version Date: 13Feb2019

Template No: CS\_TP\_BS016 Revision 4  
 Effective Date: 01Apr2016

Reference: CS\_WI\_BS005

START DATE	STOP DATE	ACTION
		- If stop date >= first IP taken date, then TEAE
	Missing	Assumed TEAE

Algorithm for Prior/Concomitant Medications:

START DATE	STOP DATE	ACTION
Known	Known	
	Partial	Impute stop date as latest possible date (i.e. last day of month if day unknown or 31st December if day and month are unknown)
	Missing	
Partial	Known	Impute start date as earliest possible date (i.e. first day of month if day unknown or 1st January if day and month are unknown)
	Partial	Impute start date as earliest possible date (i.e. first day of month if day unknown or 1st January if day and month are unknown) and impute stop date as latest possible date (i.e. last day of month if day unknown or 31st December if day and month are unknown)
	Missing	Impute start date as earliest possible date (i.e. first day of month if day unknown or 1st January if day and month are unknown)
Missing	Known	No imputation for missing start date
	Partial	No imputation for missing start date; impute stop date as latest possible date (i.e. last day of month if day unknown or 31st December if day and month are unknown)
	Missing	

Document: \\eedc-vnasc01\Biosdata\Archigen\SAIT101\YWA21301\Biostatistics\Documentation\SAP  
 Author: Version Number: V2.0  
 Version Date: 13Feb2019

Template No: CS\_TP\_BS016 Revision 4 Reference: CS\_WI\_BS005  
 Effective Date: 01Apr2016

## APPENDIX 2. DATA EXTRACTION RULE

- a. **AE** domain: take all AEs if AE start date (imputed date will be used if partial date available)  $\leq$  cut-off date  
If AE start date  $\leq$  cut-off date  $<$  AE end date (i.e., resolved after cut-off date), then the AE will be considered as “Ongoing” for reporting. AE outcome will programming changed as “NOT RECOVERED/NOT RESOLVED”
- b. **CM** domain: take all CMs if CM start date (imputed date will be used if partial date available)  $\leq$  cut-off date  
If CM start date  $\leq$  cut-off date  $<$  CM end date (i.e., medication ended after cut-off date), then the CM will be considered as “Ongoing” for reporting.
- c. **Other** domains:  
Use --DTC or --STDTC depending on domain  
Take all data if --DTC or --STDTC  $\leq$  cut-off date

---

Document: \\ieedc-vnasc01\Biosdata\Archigen\SAIT101\YWA21301\Biostatistics\Documentation\SAP  
Author: Version Number: V2.0  
Version Date: 13Feb2019

Template No: CS\_TP\_BS016 Revision 4 Reference: CS\_WI\_BS005  
Effective Date: 01Apr2016

## APPENDIX 3. PROTOCOL DEVIATION SPECIFICATION

Deviation code	DVDECOD (Category)	*****Sample*****	Additional Description for PD detection	Study Part	Timepoint	DVCAT	program/ Source data verification?	Excluded from the PP	Excluded from the PP2	Excluded from the PK	Excluded from the PD
		DVTERM (PD Description)									
I01	Eligibility and Entry Criteria	Male or female age out of range (< 18 or >80 years) at Screening		A, B	Screening	Major	program	Yes	Yes		
E01	Eligibility and Entry Criteria	Previous usage of any biological agents including any TNF-alpha inhibitor prior to Randomisation	Refer ATC CODE for prohibited medication to get this PD.		Week 0 (Randomisation)	Major	program	Yes	Yes		
D01	Withdrawal Criteria	Subject still receive IPs even though serious infection including active TB or opportunistic infection	from adverse event data; if not, source data verification		All visits from Randomisation	Major	program and manual review	No	No		
C01	Study Procedures Criteria	More than 6 weeks from Screening to randomisation (+1 week window allowed if the subject is still eligible at the Randomisation for ESR/CRP and major safety lab)	More than 6 weeks from Screening to randomisation (+1 week window allowed if the subject is still eligible at the Randomisation for ESR/CRP and major safety lab)		Week 0 (Randomisation)	Major	program and manual review	Yes	Yes		
C02	Study Procedures Criteria	Week 24/Visit8 window deviation (out of +- 5 days)	Week 24/Visit 8 window deviation (out of +- 5 days)		Week 24/Visit 8	Major	program and manual review	No	No		
C18	Study Procedures Criteria	ACR component (CRP) assessed after IP injection at Randomisation	ACR component (CRP) assessed after IP injection at Week 0 (Randomisation) regardless IP time is unknown or missing		Week 0	Major	Source data verification	Yes	Yes		
C20	Study Procedures Criteria	Chest x-ray assessed earlier than 3 months prior to Screening or after Randomisation; If >100 days prior to Screening or after Randomisation, exclude from PPS1 and PPS2	Chest x-ray assessed earlier than 3 months prior to Screening or after Randomisation; If >100 days prior to Screening or after Randomisation, exclude from PPS1 and PPS2		Week 0	Major	program and source data verification	Yes, if >100 days prior to Screening or after Randomisation	Yes, if >100 days prior to Screening or after Randomisation		

Document: \\eedc-vnasc01\Biosdata\Archigen\SAIT101\YWA21301\Biostatistics\Documentation\SAP  
 Author: Version Number: V2.0

Version Date: 13Feb2019

Template No: CS\_TP\_BS016 Revision 4  
 Effective Date: 01Apr2016

Reference: CS\_WI\_BS005

## APPENDIX 4. DETAIL OF MULTIPLE IMPUTATION FOR MISSING AT RANDOM

```
proc mi data = formi2 nimpute = 100 seed = 12345 out = bocfmil minimum = 0;  
  by trt01pn trt01p;  
  var param1_1 param2_1 param3_1  
      param1_2 param2_2 param3_2  
      param1_3 param2_3 param3_3  
      param1_4 param2_4 param3_4;  
  mcmc chain = multiple impute = monotone;  
run;
```

```
proc sort data = bocfmil;  
  by _imputation_ trt01pn usubjid;  
run;
```

```
proc mi data = bocfmil out = bocfmi2 nimpute = 1 seed = 12345 minimum = 0;  
  by _imputation_;  
  var trt01pn param1_1 param2_1 param3_1  
      param1_2 param2_2 param3_2  
      param1_3 param2_3 param3_3  
      param1_4 param2_4 param3_4;  
  monotone regression;  
run;
```

```
****Get LS means and CI;  
%macro m_ancova_mi(trtn = , outn = , avar = );
```

```
ods output SolutionF = _pval_mi Diffs = _lsmeand_mi LSMeans = _lsmean_mi;
```

```
proc mixed data = ADBOCFMI;  
  by _imputation_;  
  where &trtn in (&trtn.);  
  class &trtn;  
  model &avar. = &trtn avalb / solution;  
  lsmeans &trtn / cl pdiff ;  
run;
```

```
proc mianalyze parms(classvar = full) = _lsmean_mi;  
  class &trtn;  
  modeleffects &trtn;  
  ods output parameterestimates = lsmean_&outn.;  
run;
```

```
proc mianalyze parms(classvar = full) = _lsmeand_mi;  
  class &trtn;  
  modeleffects &trtn;  
  ods output parameterestimates = lsmeand_&outn.;  
run;
```

```
proc mianalyze parms = _pval_mi;  
  class &trtn;  
  modeleffects &trtn avalb;  
  ods output parameterestimates = pval_&outn.;  
run;
```

Document: \\eedc-vnasc01\Biosdata\Archigen\SAIT101\YWA21301\Biostatistics\Documentation\SAP  
Author:

Version Number: V2.0  
Version Date: 13Feb2019

Template No: CS\_TP\_BS016 Revision 4  
Effective Date: 01Apr2016

Reference: CS\_WI\_BS005

```
%mend m_ancova_mi;
```

```
****<AVAL>;
```

```
****<SAIT101 vs MabThera>;
```

```
%m_ancova_mi(trtn = 1 2, outn = 1, avar = aval);
```

---

Document: \\ieedc-vnasc01\Biosdata\Archigen\SAIT101\YWA21301\Biostatistics\Documentation\SAP

Author:

Version Number:

V2.0

Version Date:

13Feb2019

Template No: CS\_TP\_BS016 Revision 4  
Effective Date: 01Apr2016

Reference: CS\_WI\_BS005

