### 15.1. MAIN EFFICACY

#### 15.1.1. MAIN EFFICACY VARIABLE & DERIVATION

The main efficacy variable is the change from Baseline in DAS28-CRP at Week 24. The change from baseline in DAS28-CRP at Visit 24 will be calculated as follows:

Change at Visit 24= Value of DAS28-CRP at Visit 24 – Baseline value of DAS28-CRP

DAS28-CRP assessments consisted of tender joint counts (TJC), swollen joint counts (SJC) and C-reactive Protein (CRP). Formula is listed as follow or a calculator is available online at the following website: <http://www.das-score.nl/das28/DAScalculators/dascalculators.html>.

- $DAS28-CRP = [0.56 \times \sqrt{(TJC28)} + 0.28 \times \sqrt{(SJC28)} + 0.36 \times \ln(CRP+1)] \times 1.10 + 1.15$

TJC28: Tender Joint Count (28 joints); SJC28: Swollen Joint Count (28 joints); CRP(mg/L).

28 joints include proximal interphalangeal joints (10 joints), metacarpophalangeal joints (10 joints), wrists (2 joints), elbows (2 joints), shoulders (2 joints) and knees (2 joints).

DAS28-CRP will be considered missing if any of the three components is missing.

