- For patients with missing DAS28-CRP at Week 24 due to treatment-related reasons, i.e. treatment discontinuation for receiving rescue therapy OR adverse events OR lack of efficacy before Week24, the BOCF approach will be applied. Otherwise, multiple imputation for missing at random approach will be applied. In order to preserve any observed difference between treatment groups, best change will be assumed to be missing at random (MAR). Robustness of the main efficacy conclusion to the missing at random assumption will be evaluated by sensitivity analyses that will take account the reasons for withdrawal.

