##### 15.1.4.1. Multiple imputation for missing at random

Monotone missing data structure will be created as follows: intermediate (non-monotone) missing data will be multiply imputed using the Markov chain Monte Carlo (MCMC) method and assuming MAR and multivariate normality. Transformation of data will only be used if there is a clear deviation from normality. The SAS procedure PROC MI with the MCMC option will be used with seed number=12345.

Then, each component will be imputed with treatment group, DAS28-CRP at baseline and data at previous visit from all DAS28-CRP components as covariates.

Imputation will be repeated 100 times. The DAS28-CRP will then be calculated for each of the multiply imputed data sets from the imputed components. Results will be combined using MIANALYZE SAS procedure with the Rubin's rules. Please refer to [Appendix 4](#) for detail SAS code.

---

Document:	\\ieedc-vnasc01\Biosdata\Archigen\SAIT101\YWA21301\Biostatistics\Documentation\SAP	Version Number:	V2.0
Author:		Version Date:	13Feb2019
Template No:	CS_TP_BS016 Revision 4	Reference:	CS_WI_BS005
Effective Date:	01Apr2016		

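### SAP 15.1.4.1 and Appendix 4: imputing the DAS28-CRP components on what appears to be the raw scale, from a normal model cut at 0, pushes imputed Week 24 scores upward; impute on the square-root and log scales instead

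*SAP*

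**What the plan says.** SAP 15.1.4 lists four ways of filling in missing Week 24 scores: LOCF, BOCF, BOCF for treatment-related reasons only, and BOCF for treatment-related reasons with multiple imputation for the rest: "Otherwise, multiple imputation for missing at random approach will be applied".

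For that last analysis, section 15.1.4.1 works on the components: "each component will be imputed with treatment group, DAS28-CRP at baseline and data at previous visit from all DAS28-CRP components as covariates". The model is specified as "assuming MAR and multivariate normality", and the score is rebuilt afterwards: "The DAS28-CRP will then be calculated for each of the multiply imputed data sets from the imputed components". On scale, the section says only this: "Transformation of data will only be used if there is a clear deviation from normality". It names no test, threshold, scale or point at which that would be decided.

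Appendix 4 prints the program. Both PROC MI steps set a minimum of 0. Neither sets a maximum and neither transforms a variable. The second step reads "proc mi data = bocfmil out = bocfmi2 nimpute = 1 seed = 12345 minimum = 0".

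SAP 15.1.1 defines DAS28-CRP from the square roots of TJC28 and SJC28 and the log of CRP+1. SAP 15.1.2 leaves the main analysis on available data, without imputation.

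**The concern.** Values are drawn on one scale and scored on another. Joint counts and CRP after treatment are right-skewed and can lie close to zero. A normal model with a residual SD that is large relative to the predicted value puts mass below 0. Redrawing that mass raises the mean, and the normal shape supplies too few of the small values that a skewed variable would have. The square roots and the log then turn this into an upward error in the imputed score. Nothing prevents an imputed joint count above 28.

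Of the four missing-data methods, this is the only one that uses missing-at-random imputation. A robustness check should not bring in an error of its own, least of all one that fails to cancel when the arms lose different numbers of patients.

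**Working it through.** **Inputs from the documents.** SD 1.0, margin ±0.6, 2.5% per one-sided test, 94 per group (FAS) and about 77 per group (PP), 18% withdrawal, stated power 96% and about 91% (SAP 2.3); the DAS28-CRP formula (SAP 15.1.1); the program (Appendix 4).

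**Assumptions.** That `param1` to `param3` are the raw components is inferred from SAP 15.1.1 and 15.1.4.1, because the code does not label them. `minimum = 0` is taken to redraw values below 0. The Week 24 distributions are assumed: TJC28 mean 3.5–10, SJC28 2.2–7, CRP 7–16 mg/L, right-skewed, correlation between visits 0.5–0.9.

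1. **The plan's own figures.** Power = 2Φ(0.6/(SD·√(2/n)) − 1.96) − 1.
   - n = 94: 0.6/0.1459 = 4.11, so 2Φ(2.15) − 1 = 96.9% (96.7% with t), against 96% stated.
   - n = 77: 0.6/0.1612 = 3.72, so 2Φ(1.76) − 1 = 92.2% (91.8% with t), against about 91% stated.
   - Both are reproduced to within 2 points.

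2. **The natural scale.** Multiplying out the formula gives DAS28-CRP = 0.616·√TJC28 + 0.308·√SJC28 + 0.396·ln(CRP+1) + 1.15. The score is exactly linear in the transformed components.

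3. **Why the cut raises the mean (illustrative numbers).** Take a predicted count of 4 with residual SD 4, redrawn below 0. The mean becomes 4 + 4·φ(1)/Φ(1) = 4 + 4 × 0.242/0.841 = 5.15.

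4. **Simulation of the monotone step.** Three arms of 94, four visits and 18% dropout. Bias is the imputed minus the true Week 24 score among dropouts. Selected scenarios (Monte Carlo SE 0.009–0.019):

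| Assumed Week 24 score; SD of change | As printed | √/ln scale, floor kept | √/ln scale, no floor |
|---|---|---|---|
| 4.55; 0.81 (narrow spread) | +0.092 | −0.001 | −0.006 |
| 4.70; 1.00 | +0.272 | +0.027 | +0.009 |
| 4.00; 0.97 | +0.491 | +0.040 | +0.016 |
| 3.21; 1.00 (many zero counts) | +0.726 | +0.140 | −0.031 |
| 3.20; 1.23 (many zero counts) | +0.850 | +0.226 | 0.000 |

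   Over all scenarios the bias is +0.09 to +0.85 as printed, and +0.26 to +0.73 where the SD of change is about 1.0, as the SAP presumes. On the transformed scale it is −0.02 to +0.23 with the floor kept and −0.04 to +0.02 without it. A second simulation gave 0.27 to 0.47 as printed, about 0.00 to 0.11 with the floor and −0.02 to +0.02 without.

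5. **Carried into the treatment difference.** With 18% imputed, an arm mean moves by 0.18 × 0.09 ≈ 0.02 up to 0.18 × 0.85 ≈ 0.15.
   - Equal dropout, no true difference: the shift is within about 0.01 (SE 0.004–0.009). In one setting with a true difference, 0.57 became 0.55.
   - 25% against 10%: shift ≈ bias × 0.15. For bias 0.36, 0.454 and 0.593 this gives 0.05, 0.07 and 0.09. The last two were simulated directly at +0.068 and +0.091. On the transformed scale these fall to +0.010 and +0.018 with the floor, and to +0.001 and −0.001 without it.

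6. **Against the margin.** Under the step 1 assumptions, a shift of 0.07 would lower the chance of falling inside ±0.6 from 96.9% to 94.9% (n = 94) or from 92.2% to 89.4% (n = 77), in this sensitivity analysis only.

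The MCMC step for intermittent gaps was not simulated.

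**The case against.** The strongest reply is that little depends on this analysis. The main analysis must succeed in both FAS and PP, and it imputes nothing. The imputation is one of four sensitivity analyses, with no decision rule attached, and it covers only scores missing for reasons that are not treatment-related. Under the protocol, patients who stop treatment or receive rescue still attend visits to Week 52, so fewer than 18% of Week 24 scores may be missing. If only half of the missing scores reached multiple imputation (an assumption), the smallest shift in step 5 would halve, from about 0.05 to about 0.03. Dropout of 25% against 10% is also lopsided for a double-blind comparison of a proposed biosimilar with its reference. All of this stands, and it limits the consequence.

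It can also be said that the SAP already allows a transformation, and that the printed code is incomplete and might be fed transformed values. This stands only in part. The clause has no trigger and no named scale, the printed program does not implement it, and the skew of counts and CRP is foreseeable. The choice is therefore left to discretion in a check that is meant to be pre-specified.

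Three stronger readings are tempting and are not supported. A reader might infer a fixed bias, such as 0.2 to 0.4 units; the documents give no Week 24 component distributions from which any single figure could follow. A reader might infer that the equivalence conclusion is at risk; SAP 15.1.2 excludes imputation from that analysis. A reader might infer that rescaling alone cures the problem; with the floor kept, up to about 0.1 to 0.2 remains when many counts are zero.

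**Conclusion.** The point holds as a flaw in the specification of one sensitivity analysis. As printed, and reading the parameters as raw components, imputed Week 24 scores are biased upward in every scenario examined, by roughly 0.1 to 0.85 units depending on the assumed distributions. The effect on SAIT101 minus MabThera is about 0.01 to 0.02 with equal dropout. It is about 0.05 to 0.09 with 25% against 10% dropout if all missing scores are multiply imputed, which at most is 0.09/0.6 = 15% of the margin; the arm that loses more patients looks worse. The direction follows from the method. The size rests on assumed distributions and on simulation of the monotone step alone. The main equivalence analysis, the planned sample size and its power are unaffected. The change is worth making because a plainly better scale is available at almost no cost.

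**What to change.** Before unblinding, amend SAP 15.1.4.1 and Appendix 4 together:

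- Create sqrt(TJC28), sqrt(SJC28) and ln(CRP+1) at each visit and use them in both PROC MI steps in place of the raw components.
- Remove `minimum = 0` from both steps.
- Compute DAS28-CRP directly as 0.616, 0.308 and 0.396 times the imputed transformed values, plus 1.15. Do not back-transform first, because squaring would turn a negative draw into a positive count.
- Replace the conditional transformation clause with this rule, so that text and code agree.

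This also settles a smaller mismatch. The text names baseline DAS28-CRP as a covariate, but the printed variable list does not contain it. Once the baseline components are entered on the transformed scales, baseline DAS28-CRP is an exact linear combination of them and need not be added.

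The 100 imputations, the seed, the ANCOVA and the combination by Rubin's rules can stay. The cost is a few lines of SAS and one SAP sentence, with no extra patients. The drawback is that an individual imputed component may fall slightly outside its possible range.

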## APPENDIX 5. DETAIL OF PORPORTION DIFFERENCE IN LOGISTICS REGRESSION

The analysis of the observed proportion difference will be based on logistic regression with subsequent transformation of the estimated parameters to the difference in proportions. The estimates from the logistic regression are on the logit scale, and the difference in proportions will be calculated as the difference between the predicted probabilities in the treatment groups on the original scale.

The method of Reeve for calculating the confidence interval will now be described in detail. We will parameterize the model in the form

$$L(E(Y_i)) = \beta_0 + \gamma\tau_i + \beta_1x_{i1} + \dots + \beta_kx_{ik}.$$

$$z = b_0 + b_1x_1^* + \dots + b_kx_k^*$$

g =  $\gamma$  the treatment group effect.

Let  $b_0, g, b_1, \dots, b_k$ , be the maximum likelihood estimates for the parameters. Then the estimator for the difference in proportions between the treatment groups can be estimated as

$$\Delta p = h(b_0 + g + b_1x_1^* + \dots + b_kx_k^*) - h(b_0 + b_1x_1^* + \dots + b_kx_k^*),$$

$x_k^*$  is the mean value of  $x_{ik}$  over the i-subjects.

where  $h = L^{-1}$ . For ease of exposition, define  $z = b_0 + b_1x_1^* + \dots + b_kx_k^*$ , and define  $p_\tau = h(z + g\tau)$  for  $\tau = 0$  or  $1$ . We then have  $\Delta p = p_1 - p_0$ . Then confidence limits  $x_A$  for  $A = 0.025$  or  $0.975$  for 95% CIs and for  $A = 0.05$  or  $0.95$  for 90% CIs is given by  $x_A = F\Delta p(A)$ , where  $F\Delta p(A)$  denotes the cumulative distribution function of  $\Delta p$ . This distribution function may be calculated directly using a Monte Carlo method, by simulating  $K$  realizations of  $(g, z)$  from the appropriate bivariate Normal distribution, and for each realization calculating the statistic  $T(g, z) = h(g + z) - h(z)$ . Let  $\theta \equiv (\bar{g}, \bar{z})$ , and  $R$  the Cholesky decomposition of  $\text{Var } \theta$ . If  $X$  is a  $K \times 2$  matrix, each element of which is independent, normally distributed with mean 0 and variance 1,  $\Theta = XR + \theta$  follows the appropriate  $(g, z)$  distribution. The cumulative density function of  $T(g, z)$  can then be generated, and the appropriate tail probabilities found.

The analysis will consist of the following two steps: (take ACR20 for example)

Step 1: Calculation of difference in proportion based on adjusted proportion

The adjusted difference of proportion in each group is estimated from the logistic regression on the logit scale. The difference in proportions is calculated as the difference between the probabilities predicted by the model for both treatment groups on the original scale.

**Details:**

The statistical model for the analysis of the ACR20 will be:

$$(M2) \text{ Logit } (E\{\text{ACR20}\}) = \text{treatment} + \text{baseline DAS28-CRP}$$

The following SAS code will be used:

```
PROC GENMOD DATA= ACR20_central;
CLASS TRT;
MODEL response (event='Y') = TRT base-DAS28-CRP / dist=bin link=logit;
lsmeans TRT / ilink;
run;
```

The population adjusted natural scaled proportion are the estimates produced by the LSMEANS statement.

Step 2: Calculation of confidence intervals based on cumulative distribution function method of Reeve

The respective risk-difference confidences intervals are calculated using the risk difference (calculated in Step 1) and the cumulative distribution function method of Reeve with 1,00 simulations.

